4.6. Duration of Study Participation

The maximum time of study participation for a patient is up to 26 months, including the screening period (up to 28 days), treatment administration period (up to 24 months; see Section [4.2.1](#)), and safety follow-up period (30 \pm 5 days after the last dose).

5. PATIENT POPULATION

5.1. Number of Patients

Approximately 70 patients are anticipated for enrollment, which provides for 4 to 7 dose-finding cohorts in Arm 1, 1 to 5 cohorts in Arm 2, and replacement of 1 patient per cohort, as well up to 20 additional patients enrolled at the RP2D in Arm 2. Additional cohorts may be required in either arm to determine the MTD/RP2D.

5.2. Selection of Patients

5.2.1. Eligibility Criteria

This study will comprise patients with advanced/metastatic solid tumors or lymphoma. Patients will be eligible for enrollment regardless of gender or race/ethnicity.

5.2.1.1. Inclusion Criteria

Patients must meet all of the following inclusion criteria to be eligible:

1. Able and willing to voluntarily complete the informed consent process (patient or patient's representative).
2. Adults aged ≥ 18 years (on the day of signing informed consent) with histologically- or cytologically-confirmed stage III or IV advanced/metastatic solid tumor or lymphoma for which no therapeutic options are available to extend survival or for which the patient is not a candidate for standard-of-care therapy.
3. Eastern Cooperative Oncology Group performance status ≤ 1 .
4. Life expectancy ≥ 3 months.
5. ≥ 1 injectable, measurable (≥ 10 mm in diameter, or ≥ 15 mm for nodal lesions), eligible lesion as defined by RECIST 1.1 ([Eisenhauer et al 2009](#)), iRECIST ([Seymour et al 2017](#)), and/or LYRIC ([Cheson et al 2016](#)) and as assessed by the Investigator. Eligible lesions must not be located in the thoracic cavity, spleen, pancreas, gastrointestinal tract (liver injection allowed), or cranium and must be amenable to percutaneous injection and away from major blood vessels or neurological structures.
6. Able to provide biopsies for biomarker analysis from injected and (if available) noninjected lesions at baseline and other time points during the study.
7. Oxygen saturation $> 90\%$ without the use of supplemental oxygen.
8. Adequate cardiac function, defined as follows:
 - a. Left ventricular ejection fraction (LVEF) $> 50\%$ by multi-gated acquisition (MUGA) scan or echocardiogram (ECHO) performed within 6 months prior to the first dose of study treatment provided the patient has not received any potential cardiotoxic agents in the intervening period. Symptoms relating to left ventricular dysfunction, cardiac arrhythmia, or cardiac ischemia must all be Grade < 1 per NCI CTCAE version 5.0.
 - b. QTc interval corrected for heart rate using Fridericia's formula (QTcF) < 480 msec at screening.

9. Laboratory values within the following ranges:

- Absolute neutrophil count $\geq 1500/\mu\text{L}$
- Lymphocyte count $\geq 500/\mu\text{L}$
- Platelets $\geq 100,000/\mu\text{L}$ without transfusion
- Hemoglobin $\geq 9.0 \text{ g/dL}$ (patients may be transfused to meet this criterion)
- Estimated glomerular filtration rate (eGFR) $> 50 \text{ mL/min}/1.73 \text{ m}^2$ per the Cockcroft-Gault formula
- Total bilirubin $\leq 1.5 \times$ the upper limit of normal (ULN) OR direct bilirubin \leq ULN for participants with total bilirubin levels $> 1.5 \times$ ULN or $\leq 3 \times$ ULN for patients with Gilbert's syndrome
- AST, ALT, and alkaline phosphatase $\leq 2.5 \times$ ULN (AST and ALT $\leq 5 \times$ ULN for participants with liver metastases and alkaline phosphatase $\leq 5 \times$ ULN for participants with liver or bone metastases)
- International normalized ratio (INR) or PT or aPTT $\leq 1.5 \times$ ULN unless participant is receiving anticoagulant therapy as long as PT or aPTT is within therapeutic range of intended use of anticoagulants

10. Agree to use an acceptable method of contraception after informed consent, throughout the study, and for 5 months after the last dose of SYNB1891 or atezolizumab.

Additional inclusion criteria that apply only to Arm 2 study participants are as follows:

11. TSH must be within the normal reference range or the patient must be receiving stable thyroid replacement therapy.
12. Patients must have received treatment with an anti-PD-1/L1 monoclonal antibody (mAb) administered either as monotherapy, or in combination with other CPIs or other therapies, if indicated (if CPI therapy is not indicated as a part of standard-of-care therapy, patients may be CPI naïve).

Additional inclusion criteria that apply only to the Arm 2 expansion study participants are as follows:

13. Patients must have progressed on treatment with an anti-PD-1/L1 mAb administered either as monotherapy, or in combination with other CPIs or other therapies, if indicated (if CPI therapy is not indicated as a part of standard-of-care therapy, patients may be CPI naïve).

PD-1/L1 treatment progression is defined by meeting all of the following criteria:

- a. Has received at least 2 doses of an approved anti-PD-1/L1 mAb.
- b. Has demonstrated disease progression after PD-1/L1 as defined by RECIST 1.1, iRECIST, and/or LYRIC. The initial evidence of disease progression is to be confirmed by a second assessment no less than 4 weeks from the date of the first documented disease progression, in the absence of rapid clinical progression as determined by the Investigator. Once disease progression is confirmed, the initial date

of disease progression documentation will be considered the date of disease progression.

- c. Progressive disease has been documented within 12 weeks from the last dose of anti-PD-1/L1 mAb.

5.2.1.2. Exclusion Criteria

Patients meeting any of the following criteria are not eligible for study enrollment:

1. Chemotherapy, radiation, or biological cancer therapy within 14 days prior to the first dose of study treatment, or failure of any AEs to recover to Baseline or NCI CTCAE version 5.0 Grade 1, except for any grade of alopecia caused by cancer therapeutics administered > 28 days earlier.
2. Systemic immunostimulatory agents (including, but not limited to, IFN and IL-2) within 28 days or 5 drug elimination half-lives (whichever is longer) prior to initiation of study treatment. Checkpoint inhibitors are not considered systemic immunostimulatory agents for this criterion and are subject to the washout period listed in exclusion criterion #1.
3. Allogeneic hematopoietic stem cell transplantation that requires current use of immunosuppressors.
4. Receipt of a live vaccine within 90 days prior to the first dose of study treatment or anticipation of a need for such a vaccine during treatment.
5. Receipt of antibiotics within 7 days prior to the first dose of study treatment.
6. Participation in a study of an investigational agent and receipt of study therapy or use of an investigational device within 28 days prior to the first dose of study treatment.
7. Diagnosed immunodeficiency or current use of chronic systemic steroid therapy in excess of replacement doses (prednisone \leq 10 mg/day or equivalent is acceptable) or any other form of immunosuppressive medication within 7 days prior to the first dose of study treatment.
8. For injection and biopsy of visceral (deep) lesions: patients must not be on long-acting antiplatelet agents such as aspirin or clopidogrel or on therapeutic doses of anticoagulants, with the exception of patients receiving a preventative dose of low molecular weight heparin. In patients receiving preventative low molecular weight heparin, treatment must be stopped 24 hours before the intratumoral injection and resumed again 24 hours after the injection ([Marabelle et al 2018](#)).
9. Previous or concurrent malignancy, with the exception of:
 - a. Adequately treated basal or squamous cell carcinoma, in situ carcinoma of the cervix, or ductal carcinoma in situ of the breast;
 - b. Localized prostate cancer definitively treated with surgery or radiation or stable on hormone therapy;
 - c. Other cancer from which the patient has been disease free for at least 2 years.
10. Clinically active central nervous system (CNS) metastases and/or carcinomatous meningitis (treated brain metastases are permitted if radiologically stable for \geq 28 days prior to the first dose of study treatment).

11. Allergy to antibiotics that precludes treatment for infection with *E. coli* Nissle 1917 (see [Appendix 4](#) for common antibiotics to which *E. coli* Nissle is sensitive).
12. Hepatitis B or C infection(s) unless screening tests indicate a negative viral load, and/or human immunodeficiency virus (HIV) infection unless screening tests indicate a negative or below the limit of quantitation viral load.
13. Known active tuberculosis.
14. Grade 3 or higher infection according to NCI CTCAE within 28 days prior to initiation of study treatment, including, but not limited to, hospitalization for complications of infection, bacteremia, or severe pneumonia.
15. Failure to fully recover from the effects of major surgery. Surgeries that required general anesthesia must be completed > 14 days before the first dose of study drug. Surgery requiring regional/epidural anesthesia must be completed > 72 hours before the first dose of study treatment and participants should be recovered.
16. Heart failure of New York Heart Association Class 3 or greater, restrictive cardiomyopathy, or unstable angina or recent myocardial infarction within 3 months prior to the first dose of study treatment.
17. Any other medical condition that might confound the results of the study, interfere with the participant's participation, or is not in the best interest of the participant, in the opinion of the treating Investigator.
18. Pregnant or breastfeeding or anticipated conception or fathering of children within the projected duration of the study and for 5 months after the last dose of SYNB1891 or atezolizumab.

Additional exclusion criteria that apply only to Arm 2 study participants are as follows:

19. History of immune-mediated AEs on prior PD-1/PD-L1 therapies requiring discontinuation or immunosuppressor therapy, excluding endocrinopathies.
20. Active or history of underlying autoimmune disease or immune deficiency, including, but not limited to, myasthenia gravis, myositis, autoimmune hepatitis, systemic lupus erythematosus, rheumatoid arthritis, inflammatory bowel disease, antiphospholipid antibody syndrome, Wegener granulomatosis, Sjögren syndrome, Guillain-Barré syndrome, or multiple sclerosis, with the following exceptions:
 - a. Patients with a history of autoimmune-related hypothyroidism who are on thyroid replacement hormone are eligible for the study.
 - b. Patients with controlled Type 1 diabetes mellitus who are on an insulin regimen are eligible for the study.
 - c. Patients with eczema, psoriasis, lichen simplex chronicus, or vitiligo with dermatologic manifestations only (e.g., patients with psoriatic arthritis are excluded) are eligible for the study provided all of following conditions are met:
 - Rash must cover < 10% of body surface area;
 - Disease is well controlled at baseline and requires only low-potency topical corticosteroids;

- No occurrence of acute exacerbations of the underlying condition requiring psoralen plus ultraviolet A radiation, methotrexate, retinoids, biologic agents, oral calcineurin inhibitors, or high potency or oral corticosteroids within the previous 12 months.
- 21. History of a Grade ≥ 3 allergic anaphylactic reaction following treatment with a PD-1 mAb or to chimeric, human, or humanized antibodies or fusion proteins.
- 22. History of idiopathic pulmonary fibrosis, organizing pneumonia (e.g., bronchiolitis obliterans), drug-induced pneumonitis requiring treatment, or idiopathic pneumonitis, or evidence of active pneumonitis.
- 23. Known hypersensitivity to Chinese hamster ovary cell products or any component of the atezolizumab formulation.

6. INVESTIGATIONAL MEDICINAL PRODUCT AND CONCOMITANT MEDICATIONS

6.1. Investigational Product Supply and Administration

Within this protocol, “study treatment” refers to SYNB1891 and/or atezolizumab.

6.1.1. SYNB1891

Detailed instructions for the storage, handling, and administration of SYNB1891 will be provided in the Pharmacy Manual and may override instructions provided in the following protocol sections.

6.1.1.1. Manufacturing and Formulation

SYNB1891 investigational drug product is formulated in buffer composed of 15% glycerol, 5% trehalose, 10 mM Tris at pH 7.5.

6.1.1.2. Packaging and Labeling

SYNB1891 is packaged aseptically into AT-closed vials at a volume of 0.6 mL and will be labeled for clinical study use.

6.1.1.3. Shipping, Storage, and Handling

Labeled, packaged SYNB1891 will be shipped from Synlogic’s manufacturing site to a central drug vendor. SYNB1891 must be stored at $\leq -65^{\circ}\text{C}$ in a secured freezer with controlled access.

6.1.1.4. Dispensing and Administration

The manufactured SYNB1891 drug product has a concentration of 1×10^{11} live cells/mL. To obtain appropriate doses, vial(s) of concentrated drug product will be thawed and appropriately diluted to a volume of 5 mL in room temperature 5% dextrose in water for injection and held at room temperature while handling prior to administration. The time between the thaw of vials containing SYNB1891 and injection should not exceed 2 hours. If the 2-hour stability window is exceeded, discard and prepare another dose.

The preparation of SYNB1891 doses must be performed in a biosafety cabinet while wearing sterile sleeves, sterile gloves, and a facemask to minimize contamination.

Once the dilutions have been prepared, withdraw 0.3 mL of the prepared cell concentration, change the needle to the appropriate length for the tumor to be treated prior to injection, and follow local protocol to obtain the final dose volume of 0.1 mL.

6.1.2. Atezolizumab

Atezolizumab will be supplied by the manufacturer as a sterile liquid in a single-use, 20-mL glass vial and labeled and shipped to each investigational site. Atezolizumab (1200 mg/vial) will be prepared in accordance with the current Investigator’s Brochure and administered as an IV infusion at a dose of 1200 mg Q3W.

6.2. Accountability and Dosing Compliance

All doses of SYNB1891 and atezolizumab will be administered in the clinic by trained study personnel. Dosing details (e.g., lot/batch number, date/time of administration) will be documented in the eCRF.

Unless other arrangements are agreed to in writing, all unused clinical trial material should be returned to Synlogic at the completion of the study. Interim returns are permissible after drug accountability has been performed by the monitor and as agreed upon by the Sponsor.

6.3. Concomitant Medications

All concomitant medications and dietary supplements received within 28 days prior to the first dose of study treatment through 30 days after the last dose of study treatment will be recorded in the eCRFs, using generic drug names when possible.

No restrictions on concomitant medications will be implemented, other than those mentioned in the eligibility criteria (see Section 5.2.1) or the toxicity management guidelines (see Section 4.4). Concomitant medications can be administered at the Investigator's discretion to conform to standard practice during the dosing period; however, Investigators should use caution when prescribing concomitant medications, as SYNB1891 has not been previously investigated in the clinical setting. Investigators should contact the Medical Monitor(s) when they are unsure whether a drug should be prescribed to a patient. If there is a clinical indication for any medication or vaccination specifically prohibited during the study, discontinuation from study treatment may be required at the discretion of the Medical Monitor(s).

7. STUDY PROCEDURES AND ASSESSMENTS

Before recruitment of patients into the study, written Institutional Review Board (IRB) approval of the protocol, informed consent, and any additional patient information must be obtained.

The various assessments that will be conducted during this study are summarized in [Table 19](#) (Schedule of Events for Arm 1) and [Table 20](#) (Schedule of Events for Arm 2).

Detailed instructions regarding sample collection, shipping, and handling, as well as all laboratory procedures, will be provided to the study site in separate study manuals. Site-specific handling instructions for hematology and clinical chemistry samples should be followed.

7.1. Screening

For both study arms, screening procedures must be performed to determine eligibility for enrollment within 28 days prior to the first dose of study treatment. If a particular assessment is repeated, the results obtained closest to the first dose of study treatment should be used to assess eligibility.

During screening, a unique identification number will be assigned to each patient who signs informed consent for the study. If a patient meets all the inclusion criteria and none of the exclusion criteria and is selected to participate in the study, s/he will be enrolled and only be identified by the unique identification number.

The Investigator or designee is responsible for verifying that the patient is eligible before requesting an identification number. At the site, the Investigator will maintain a log for all screened patients (including patients who failed screening after signing informed consent) and all enrolled patients. Patients may be re-screened. Eligibility assessments from the initial screening may only be used for re-screening if performed within the screening period as defined in the protocol or within 14 days following the screening period only after consultation with the medical monitor.

Patients must be dosed within 5 calendar days of the registration/enrollment date (i.e., the date that a patient is assigned to a given dose cohort).

7.2. Safety Assessments

7.2.1. Medical History

Past and present medical history, including prior cancer diagnoses, will be recorded. Any ongoing condition and signs and symptoms observed prior to signing of the informed consent should be recorded as medical history.

7.2.2. Adverse Events

Adverse events will be assessed continuously by direct observation and patient interviews. The severity of AEs will be evaluated using the NCI CTCAE, version 5.0 ([US DHHS 2017](#)). All AEs occurring from the time a patient signs informed consent through the Safety Follow-up visit (30 ± 5 days after the last dose of study treatment) will be recorded, regardless of causality. After the Safety Follow-up visit, only SAEs that are considered related to study treatment will be recorded, if clinically indicated.

Postdose monitoring for AEs will be performed as described in Section 4.2.2, including telephone contact on Cycle 1 Day 3 to monitor for signs of cytokine release syndrome (see Section 4.4). If these symptoms are present, patients will be instructed on the appropriate next steps.

7.2.2.1. Monitoring for Signs and Symptoms of Infection

If clinical presentation warrants, including but not limited to cases in which patients develop persistent (> 24 hours) fever or a change in vital signs suggestive of clinical infection resulting from a study treatment or procedure, then blood and urine cultures (performed and analyzed locally) will be performed and weight will be recorded.

If a patient is treated for systemic infection such that blood culture tubes are drawn locally, an additional blood culture tube should be drawn for analysis for the presence of SYNB1891, if possible. For this purpose, patients will be provided with an identification card containing study contact information (see Central Laboratory manual for collection, shipping, and other processes).

7.2.3. Vital Signs

Vital signs (systolic blood pressure, diastolic blood pressure, body temperature, pulse, and pulse oximetry) will be collected while patients are in a seated or supine position at screening, on Cycle 1 Day 1 (predose and 30 minutes, 1 hour, 2 hours, 3 hours, 6 hours, and 24 hours postdose), on all other study treatment days (predose and 30 minutes, 1 hour, 2 hours, 3 hours, and 6 hours postdose), at EOT/Early Termination and Safety Follow-up, and as clinically indicated (see [Table 19](#) and [Table 20](#)). A ± 15-minute window is permitted at all time points.

7.2.4. Physical Examination

Complete physical examinations will be performed by trained medical personnel at screening and Baseline, with symptom-directed physical examinations performed at subsequent time points (see [Table 19](#) and [Table 20](#)). Height will be collected at screening only, and weight will be collected at the time points indicated in [Table 19](#) and [Table 20](#). Any abnormal findings will be recorded as AEs.

As a part of the physical examination and prior to each dose, a photograph of the visible injected and/or noninjected lesion(s) should be taken at the discretion of the Investigator.

7.2.5. Clinical Laboratory Measurements

Clinical laboratory tests will be performed (predose unless otherwise specified) at the time points indicated in [Table 19](#) and [Table 20](#). Baseline laboratory measurements do not need to be repeated if screening measurements were performed within 3 days prior to Cycle 1 Day 1.

Screening for HIV and hepatitis B and C will also be performed prior to study dosing. Serum pregnancy testing will be performed at screening, with urine pregnancy testing performed at subsequent time points (see [Table 19](#) and [Table 20](#)).

Screening results will be assessed by the Investigator for inclusion of patients in the study. Additionally, unscheduled clinical laboratory tests can be obtained at any time during the study

at the Investigator's discretion. The diagnosis corresponding to any clinically significant abnormality, or abnormality requiring treatment/intervention, must be recorded as an AE.

7.2.5.1. Local Laboratory Measurements

[Table 17](#) outlines the clinical laboratory measurements that will be reviewed at the local laboratory.

On dosing days, prior to receiving study treatment, patients must meet the laboratory value criteria outlined in Section [5.2.1.1](#), with the exception that platelets may be $\geq 75,000/\mu\text{L}$ without transfusion and hemoglobin may be $\geq 8.5 \text{ g/dL}$ (patients may be transfused to meet this criterion).

Table 17: Local Laboratory Parameters

Panel	Parameters	
Hematology	Must be Reviewed Pre-dose:	
	Calculated absolute neutrophil count	
	White blood cell	Neutrophils
	Red blood cell	Lymphocytes
	Red cell indices	Monocytes
	Hemoglobin	Eosinophils
	Hematocrit	Basophils
	Platelet count	
Chemistry	Must be Reviewed Pre-dose:	
	Calcium	Alkaline phosphatase
	Chloride	Aspartate aminotransferase
	Total protein	Alanine aminotransferase
	Potassium	Lactate dehydrogenase
	Glucose	Direct bilirubin
	Sodium	Indirect bilirubin
	Blood urea nitrogen	Total bilirubin
	Creatinine	
	Bicarbonate	
	Albumin	
	Uric acid	
	Phosphorus	
	Magnesium	
Thyroid Function	May be Reviewed Pre- or Postdose:	
	Free T4	Thyroid-stimulating hormone
Coagulation	May be Reviewed Pre- or Postdose:	
	Prothrombin time and/or activated partial thromboplastin time	
	International normalized ratio	
Urinalysis	May be Reviewed Pre- or Postdose:	
	Dipstick:	Microscopic (if dipstick is positive):
	pH	White blood cell count
	Glucose	Red blood cell count
	Protein	Casts
	Bilirubin	
	Ketones	
	Leukocytes	
	Blood	

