7.6. Sample Retention for Exploratory Analyses

De-identified blood samples may be stored for future analyses related to cancer and immune responses for up to 5 years from the time the sample is collected. Any unused samples will be destroyed.

Table 19: Schedule of Events (Arm 1)

Study Period	Protocol Section	Screening	Cycle 1							Cycles 2-4	Additional Cycles ¹	EOT/Early Termination Visit	Safety Follow-up Visit
Study Day	7	-28 to 0	1			2 (24 ± 2 hours postdose)	3 (48 ± 2 hours postdose)	8 ± 1 day	15 ± 1 day	1 ± 1 day	1 ± 1 day	Within 14 days after last dose	30 ± 5 days after last dose
			Baseline (predose)	Dose	(6 ± 1 hours postdose)								
Informed consent/enrollment	7.1	●											
Medical history	7.2.1	●											
Physical examination	7.2.4	●	●			●		●	●	●	●	●	●
Height	7.2.4	●											
Weight	7.2.4	●	●			●				●	●	●	●
Vital signs (blood pressure, body temperature, pulse, and pulse oximetry) ²	7.2.3	●	●		●	●		●	●	●	●	●	●
Screening for hepatitis B, C and HIV	7.2.5	●											
ECGs	7.2.6	●											
MUGA/ECHO	7.2.7	●											
Hematology (CBC with differential)	7.2.5.1	●	●					●	●	●	●	●	●
Blood chemistry, including LFTs	7.2.5.1	●	●					●	●	●	●	●	●
Coagulation (PT/aPTT)	7.2.5.1	●	●					●	●	●	●	●	●
Thyroid function (FT4, TSH)	7.2.5.1	●								● ³	● ³	●	
Urinalysis	7.2.5.1	●											
Cytokine blood draw	7.2.5.2		●		●	●		● ⁴	● ⁴	● ⁴		●	
Blood preservation tube for exploratory analyses	7.2.5.2		●					● ⁵		● ^{5,6}			
Kinetics of SYNB1891 (qPCR blood assay)	7.4		●		●	●							
Serum hCG (women of childbearing potential)	7.2.5	●											
Urine hCG (women of childbearing potential)	7.2.5		●							●	●	●	
Telephone call	7.2.2						●						
Fine needle aspirate of eligible lesion pre-injection	7.4		● ⁷					● ⁵					

Study Period	Protocol Section	Screening	Cycle 1							Cycles 2-4	Additional Cycles ¹	EOT/Early Termination Visit	Safety Follow-up Visit
Study Day	7	-28 to 0	1		2 (24 ± 2 hours postdose)	3 (48 ± 2 hours postdose)	8 ± 1 day	15 ± 1 day	1 ± 1 day	1 ± 1 day	Within 14 days after last dose	30 ± 5 days after last dose	
			Baseline (predose)	Dose									
Biopsy of eligible lesion	7.4		● ⁷						● ⁸			● ⁹	
Biopsy of noninjected lesion (if applicable)	7.4		● ⁷						● ⁸			● ⁹	
Administration of SYNB1891 intratumorally	4.2			●				●	●	●	●		
Tumor response using appropriate imaging	7.3	●							● ¹⁰	● ¹⁰	●		
Adverse event reporting	7.2.2		Continuously from the time of informed consent through the Safety Follow-up visit										

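### Section 7.2.5.1 makes the coagulation limit a condition for dosing, but Table 17 in the same section lets the result be read after the injection

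*Protocol*

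**What the plan says.** The text of Protocol Section 7.2.5.1 states: "On dosing days, prior to receiving study treatment, patients must meet the laboratory value criteria outlined in Section" 5.2.1.1. It then gives two relaxations. Platelets may be as low as 75,000/µL without transfusion, and hemoglobin as low as 8.5 g/dL. Coagulation is not relaxed.

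Inclusion criterion 9 in Section 5.2.1.1 lists eight laboratory limits. The last is "International normalized ratio (INR) or PT or aPTT" at or below 1.5 × ULN. A patient on anticoagulants is accepted while PT or aPTT stays in the therapeutic range.

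Table 17, also in Section 7.2.5.1, assigns each local panel a review time. Hematology and chemistry are "Must be Reviewed Pre-dose". Coagulation (PT and/or aPTT, and INR), like thyroid function and urinalysis, is "May be Reviewed Pre- or Postdose". SAP Appendix 4 also permits postdose review of coagulation.

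Section 7.2.5 deals with when tests are done: "Clinical laboratory tests will be performed (predose unless otherwise specified) at the time points indicated in" Tables 19 and 20. Both tables schedule coagulation at every SYNB1891 injection visit.

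**The concern.** A limit that must be satisfied before treatment can only be enforced if the result is known before treatment. The text makes the clotting limit such a condition; the table removes the means of enforcing it. A site working from Table 17 can inject a patient whose INR, PT or aPTT, read afterwards, fails the stated dosing criterion.

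Two things are at stake. The first is bleeding. The product is injected percutaneously into tumor, and liver lesions are permitted: "Eligible lesions must not be located in the thoracic cavity, spleen, pancreas, gastrointestinal tract (liver injection allowed), or cranium". Exclusion 8 limits drugs that impair clotting ("patients must not be on long-acting antiplatelet agents such as aspirin or clopidogrel or on therapeutic doses of anticoagulants"), but only for visceral lesions. It does not address clotting values that have worsened since screening for another reason, such as declining liver function. For non-visceral lesions, therapeutic anticoagulation is allowed on condition that PT or aPTT is in range, and only the result can show that.

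The second is uniform conduct across about eight sites. With the same out-of-range result, one site would hold the dose and another would give it. In Cycle 1 this can reach dose-finding. Under Section 4.3.1 a dose delayed by more than 2 days is missed, and two missed doses lead to discontinuation and possible replacement. Section 4.2.3 requires a DLT or at least 2 of 3 injections for a patient to be evaluable. Dosing such a patient would also be a deviation under the text but arguably not under the table.

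**Working it through.** The plan gives no figure to reproduce. The check matches each criterion 9 limit to the Table 17 panel that supplies it and to that panel's review label.

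| Criterion 9 limit | Table 17 panel | Predose review mandatory? |
|---|---|---|
| Neutrophils | Hematology | Yes |
| Lymphocytes | Hematology | Yes |
| Platelets | Hematology | Yes |
| Hemoglobin | Hematology | Yes |
| eGFR (Cockcroft-Gault, from creatinine) | Chemistry | Yes |
| Total or direct bilirubin | Chemistry | Yes |
| AST, ALT, alkaline phosphatase | Chemistry | Yes |
| INR, PT or aPTT | Coagulation | No |

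Hematology supplies 4 and chemistry 3, so 4 + 3 = 7 limits have mandatory predose review. Coagulation supplies the remaining 1, and 7 + 1 = 8. eGFR is not itself a Table 17 entry; its laboratory input, creatinine, is.

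**Does predose sampling close the gap?** No. Section 7.2.5 fixes when the test is performed, while Table 17 fixes when the result is reviewed. A sample drawn before the injection and read after it leaves the condition unverified at the moment of dosing.

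**Does another rule settle the conflict?** No. The text names its exceptions and coagulation is not one of them. Neither document says whether the text or the table prevails.

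**Visits exposed.** Planned SYNB1891 injections in Cycles 1 to 4 are 3 in Cycle 1 (Days 1, 8 and 15) plus 1 in each of Cycles 2, 3 and 4, so 3 + 3 = 6. Coagulation is scheduled at all 6. The screening result gives some cover at Cycle 1 Day 1, which leaves 6 − 1 = 5. That cover is incomplete, because screening may be up to 28 days earlier and Section 7.2.5 waives repeat baseline tests only when screening was within 3 days. The count is therefore 5 if screening is taken as sufficient for Day 1 and 6 if it is not. Patients who continue may receive Cycles 5 to 35, which is up to 35 − 5 + 1 = 31 further Day 1 injections under the same wording.

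**The case against.** The strongest reply is that the two instructions can be followed together. Table 17 permits predose review, so a site that reads coagulation first complies with both, and a permission does not cancel a requirement. That is correct. It also means that a site using the other half of the permission risks breaching the text, so one of the two still needs correcting.

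A second reply is that the timing looks deliberate. Table 17 separates mandatory from optional panels, and SAP Appendix 4 also lets coagulation be read postdose. The fault may then lie in the broad cross-reference to Section 5.2.1.1. This is possible and the documents do not exclude it, but in that case the text is wrong and should name the exception.

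Third, the safety case is limited. Bilirubin, transaminases and alkaline phosphatase are reviewed predose and gate dosing, so much declining liver function would be caught. Predose platelet review, the limits on lesion location, Exclusion 8 and at least 6 hours of observation also help. All of this stands, and it is why the risk is modest. None of it substitutes for the clotting result. Nor would dosing-day review protect core biopsies taken up to 3 days before Cycle 2 Day 1; that is a separate matter.

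Fourth, the Arm 2 TSH limit (criterion 11) is also in Section 5.2.1.1, and Table 17 likewise allows thyroid results to be read postdose. So coagulation is the sole exception within criterion 9, not necessarily within the whole section. Criterion 9 is the most natural reading of the cross-reference, since it is the item headed as laboratory values.

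**Conclusion.** The concern holds. Section 7.2.5.1 states a dosing condition on coagulation and, in its own table, allows the result to be read too late to apply it. One of the 8 criterion 9 limits is affected, at 5 of 6 planned injections in Cycles 1 to 4 (6 of 6 without relying on screening for Day 1) and at Day 1 of every additional cycle.

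The textual conflict is certain. The clinical consequence is modest and cannot be quantified, because the documents give no frequency of out-of-range clotting values on treatment. The effect on Cycle 1 evaluability is a possible route and has not been sized. The conclusion assumes that the cross-reference means criterion 9 and that sites may act on the Table 17 label as printed. It should be fixed because the condition governs dosing and the correction is small.

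**What to change.** Change the coagulation row of Table 17 to mandatory predose review, as for hematology and chemistry. If the sponsor does not intend coagulation to gate dosing, add it to the exceptions in the Section 7.2.5.1 text beside platelets and hemoglobin. Either change removes the conflict; the first also protects the patient.

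Align the coagulation row of SAP Appendix 4. The same edit could state whether the Arm 2 TSH limit applies on dosing days, since SAP Appendix 4 requires predose review of thyroid function and Protocol Table 17 does not.

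The cost is one table row, by amendment or clarification letter. No new samples are needed, because coagulation is already scheduled at every injection visit. The burden is waiting for a local result before injecting; holding the dose for an out-of-range value is what the text already requires.
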